### II. Participant Enrollment

We anticipate phone screening up to 1000 individuals and may consent up to 100 participants in order to obtain a final sample of 42 eligible participants who complete all study sessions.

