Impulsivity/Learning Tasks: To examine medication effects on behavioral measures of impulsivity and reward-based learning (as reported in preclinical studies), participants will complete computerized cognitive tests of impulsive action, attention, and reward-based learning at the baseline session, lasting roughly 45 minutes in total duration. These measures will be repeated at follow-up visits. These tasks include: Stop Signal, Continuous Performance Test, Monetary Choice Questionnaire, Cigarette Discounting Task, Food Discounting Task, Cigarette Purchase Task, and a Reward Responsiveness Test.

The baseline session will require up to 3 hours to complete. Patients will be given breaks, snacks, and bottled water as needed.

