Medication Schedule and Safety Monitoring. Participants will receive the first 7-day supply of pills (medication or placebo, randomized and counterbalanced) at the completion of the baseline visit. In the first Phase II trial of lorcaserin for smoking cessation, the FDA-approved dose of 10mg BID (twice-daily) significantly increased abstinence relative to placebo, with a larger effect size relative to a comparison low-dose condition (10mg QD / once-daily) [51]. The BID and QD conditions were equivalent on discontinuations due to adverse events (AE; 2.5% and 3.0%, respectively) [51]. Therefore, we will use the FDA-approved dose of 10mg BID. Of note, steadystate plasma concentration occurs in 3 days. All pills will include a small amount of riboflavin to facilitate urinalysis as an index of adherence, and participants will be asked to bring their pill bottles at each visit. To monitor emergent side effects, the study staff will contact participants twice during the 7 day period (e.g., days 2 and 4). On Day 7 participants will return to complete the human laboratory session described below. This visit will also include a repeat of the medical tests/measurements (noted above), a calendar-based assessment of interim cigarette use, other substance use, and medication adherence, and a pill count. Following the laboratory visit on Day 7, participants will undergo a washout phase of at least 7 days. Next, they will repeat the same 7-day sequence in the alternate pill condition, culminating in a second, identical human laboratory session. Depending on scheduling and participant availability, we will be flexible in accommodating slight deviations from the 7-day schedules noted above, and at the discretion of the physician, participants may be provided with additional days of medication as needed. During the medication phases, side effects will be assessed with the SAFTEE questionnaire [106] and an Adverse Events Checklist [107]. Participants will complete a brief web-based assessment each morning using Redcap (link texted by research staff or automated system), including 1) prior-day number of cigarettes smoked; 2) peak prior-day craving; 3) any emergent side effects; and 4) medication adherence for the prior day. Participants will have the option of completing the brief survey via smart phone. If participants do not own a smart phone, we will provide an email link to the survey, or if preferable, a text message containing the survey questions.

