Follow-up Sessions 1 and 2. At each of two identical sessions (corresponding with the end of the medication weeks), participants will report to MRN in the morning, after receiving instructions to abstain from cigarettes (overnight) and from and alcohol (for 24 hours). Expired alveolar carbon monoxide (CO), breath alcohol concentration (BrAC), body weight, and heart rate/blood pressure will be collected at each in-person visit. Upon arrival, overnight smoking abstinence will be verified based on expired CO of <6ppm (or <50% of the initial screening reading). Participants will then provide a urine sample for riboflavin detection (as an index of adherence). A blood sample (up to 20 ml) will then be taken in order to assess metabolite levels of the medication. Blood draws will be performed by trained research staff. Participants will take that day's medication dose under supervision. Sessions will include three main elements: 1) computerized measures of impulsivity and reward sensitivity, 2) follow-up self-report (e.g., cigarette use, craving, self-efficacy) and medical (e.g., side effects, body weight) assessments, and 3) laboratory measures of smoking cue reactivity, reinstatement, and self-administration, as detailed below. The latter tasks will occur in a place equipped with a ventilated system for smoking studies.

Computerized behavioral tasks. Participants will complete validated behavioral tasks assessing impulsive action and impulsive choice, as described below. Selection of these constructs is based on preclinical observations that 5-HT2C receptor agonists reduce impulsive responding, and may preferentially influence measures of impulsive action, as opposed to impulsive choice. Because another possible mechanism by which lorcaserin influences consumptive behaviors is through reduced sensitivity to reinforcers generally [17], we will also include a validated behavioral assay of reward responsiveness. Tasks will be administered twice at the follow up visit (prior to and following the lapse procedure) to assess possible changes following nicotine exposure. These tasks include: Stop Signal, CPT, Monetary Choice Questionnaire, Cigarette Discounting Task, Food Discounting Task, Cigarette Purchase Task, and a Reward Responsiveness Test.

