Cue-elicited craving. Human studies of the effects of 5-HT2C agonists on cue-elicited drug craving have not been reported. To address this objective, we will utilize an established cue reactivity task to assess peak provoked craving (PPC). This procedure, which involves assessing craving during a cue exposure task (lighting a cigarette and attending to cues) while in a period of short-term abstinence, has been demonstrated to reliably induce acute craving [71]. Given the potential for differential medication effects on tonic vs. phasic craving [74], tonic craving will also be assessed as a component of the repeated self-report assessments (noted below).

Simulated lapse. The cue reactivity task will lead directly into the simulated lapse procedure developed by [name], who is a consultant on this project [38, 75]. Importantly, preclinical evidence shows that lorcaserin reduces both nicotine reinstatement and self-administration. The [name] paradigm is the only validated laboratory procedure that models each of these outcomes [38]. In this procedure, a nicotine deprivation period (e.g., overnight abstinence) provides a context to study medication effects on reinstatement [38]. Participants will be presented with a package of their preferred cigarettes (participants will be asked to bring one unopened pack in to the session). Participants will given the choice to initiate cigarette smoking, or to delay smoking for up to 50 minutes in exchange for monetary reinforcement. Prior studies show that a reinforcement schedule of \$1 for every 5 minutes results in participants resisting, on average, for 25 minutes, providing ideal variability in time to reinstatement [38]. If no lapse occurs (i.e., the participant resists for 50 minutes), participants will not be forced to smoke a cigarette. Following the initial decision to smoke, participants will complete assessments of craving, withdrawal, and subjective effects (described below).

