## II. Data Analysis/Statistical Considerations

Primary and secondary outcomes will be evaluated using mixed linear effects models with condition (lorcaserin, placebo) as a within-subjects factor and medication order as a between-subjects factor. Maximum likelihood estimation will be used to account for missing data by analyzing all available cases. The primary outcomes are 1) minutes of resistance to smoking reinstatement and 2) number of half cigarettes smoked during the ad lib session. Using the same model, we will also examine secondary outcomes including: impulsive choice (k value from monetary discounting task and cigarette discounting task), impulsive action (commission errors on CPT), and reward response bias as measured by the Reward Responsiveness Test.

Statistical Power. To achieve adequate power (.80) to detect medium effects of medication on our primary outcomes, we will recruit a sample of 42 smokers in order to arrive at a final sample of 34 (allowing for up to 20% attrition). Given no prior data on lorcaserin's effects on laboratory outcomes, we reviewed effects reported in similar screening studies with other medications. In a study using the lapse paradigm proposed here, varenicline had a medium to-large effect on duration to reinstatement (Cohen's d = .72) and a large effect for self-administration (d = 1.5). To account for the possibility of stronger effects for varenicline relative to lorcaserin, our power analyses assumed a medium effect size. We assumed a within-subjects correlation of 0.60 for laboratory outcomes (as reported in prior human laboratory screening studies) and an alpha level of .05. We estimated power in G\*Power software using a fixed effects, within-subjects design and two time-points. Conservatively, a sample of N = 34 allows sufficient power (.80) to detect a medium effect on the primary outcomes (Specific Aims 1 and 2). Although human data are not available to inform the predicted effect size for Aim 2, preclinical studies using this medication, and an analogous behavioral task, suggest large effects of medication. For our supplementary aim (evaluating indirect effects on the primary outcomes via impulsivity and craving), simulation studies indicate that the proposed analysis, utilizing a bootstrap procedure, will provide sufficient power (.80), given the planned sample size, to detect mediated effects in medium-to-large effect size range.

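### The crossover model names condition and order but not session: fitted as two main effects, any session 1 to session 2 change goes into the error and costs power

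*Combined protocol and SAP*

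**What the plan says.** The only statement of the model is in PROJECT DATA, II. Data Analysis/Statistical Considerations. Primary and secondary outcomes are analysed by mixed linear models with "condition (lorcaserin, placebo) as a within-subjects factor and medication order as a between-subjects factor". On missing data it says: "Maximum likelihood estimation will be used to account for missing data by analyzing all available cases". No session, visit or period term is named, and no condition-by-order interaction.

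The design is a randomised, counterbalanced two-session crossover with a washout of at least 7 days. After the first medication week and the washout, participants continue as follows: "they will repeat the same 7-day sequence in the alternate pill condition, culminating in a second, identical human laboratory session" (Medication Schedule and Safety Monitoring). In the lapse task they may "delay smoking for up to 50 minutes in exchange for monetary reinforcement" (Simulated lapse). The computerised tasks are first taken at baseline: "These measures will be repeated at follow-up visits" (Impulsivity/Learning Tasks).

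The power paragraph recruits 42 to finish with 34, allowing up to 20% attrition. Participant Enrollment instead gives a "final sample of 42 eligible participants who complete all study sessions".

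**The concern.** Two analysts could fit different models from this sentence. Read as a full within-by-between factorial, the model contains the condition-by-order interaction. In a two-session crossover that interaction is the session effect, so session is already adjusted for. Read as two main effects, it is not: order takes one value per person and says nothing about the difference between that person's two visits.

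A session change is plausible. By session 2 every participant has already done the delay-for-money task and the ad libitum smoking period once. The computerised secondary tasks, which use the same model, have been taken once before session 1. Before session 2 they have been taken three times according to the follow-up session text, or twice according to Table 1. The documents give no size or direction for such a change and describe the two sessions as identical.

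At stake are the standard error and the power of the drug comparison. If completers split unequally between orders, the estimate itself is also affected.

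**Working it through.** **Inputs from the plan.** Alpha .05 (taken as two-sided), within-subject correlation r = .60, a medium effect with no number given, 42 recruited, 34 completers, balanced allocation to order.

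**Assumed.** Drug effect τ = .5 SD. Session change π = .3 or .5 SD (not in the documents). Initial allocation 21:21.

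**The plan's own figure.** The stated power is .80 at N = 34.
- A standardised within-person difference of .5 gives power .808 at N = 34 and a minimum N of 34, an exact match.
- τ = .5 with the stated r = .60 gives .5/√(2 × .40) = .559, power .886 at N = 34 and a minimum N of 28.

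So at r = .60 there is some reserve above .80, and on the reading that reproduces N = 34 there is none.

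**Model.** The drug-minus-placebo difference has mean τ − π in drug-first participants and τ + π in placebo-first participants, with variance 2(1 − .60) = .80 in each order.
- *Without session:* one-sample t on all differences, N − 1 df. With equal orders the variance becomes .80 + π², an inflation of 1 + .09/.80 = 1.11 at .3 SD and 1 + .25/.80 = 1.31 at .5 SD. The offset in the estimate is π(n₂ − n₁)/N, where n₁ is drug-first and n₂ placebo-first completers. At 18:16 its size is 2/34 × .3 = .018 or 2/34 × .5 = .029 SD.
- *With session:* average of the two order means, variance pooled within order, N − 2 df.

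**Simulation, N = 34.** Paired entries are for π = .3 / .5 SD. *Opposes* and *favours* describe the direction of the offset relative to the drug effect.

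| Completers by order | Size of offset (SD) | Type I error, no session term | Power, no session term | Power, session term |
|---|---|---|---|---|
| 17:17 | 0 | .039 / .025 | .86 / .82 | .885 |
| 18:16, opposes | .018 / .029 | – | .84 / .76 | .884 |
| 18:16, favours | .018 / .029 | – | .885 / .86 | .884 |
| 19:15, opposes | .035 / .059 | .044 / .036 | .81 / .71 | .88 |
| 19:15, favours | .035 / .059 | .044 / .036 | .905 / .90 | .88 |
| Average over random loss of 8 from 21:21 | 0 | .041 / .030 | .859 / .811 | .883 |

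The split probabilities are hypergeometric: 17:17 .303, 18:16 .229 each way, 19:15 .097 each way, 20:14 .021 each way, 21:13 .002 each way. At 20:14 type I error is about .05.

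**The loss in completers.** With a session term, power is .864 at N = 32 and .8125 at N = 28. The averages .859 and .811 therefore cost about what losing 2 or 6 of the 34 completers would.

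**Other conditions.**
- No session change: at 17:17, .886 without and .885 with the term; averaged over splits, .885 and .883.
- Smaller changes at 17:17: power without the term is about .884 at .1 SD and about .875 at .2 SD.
- The reading that reproduces N = 34: at 17:17 power is about .78 / .73 without session and about .81 with it.
- All 42 complete (21:21): power .93 / .90 without session and .94 with it; type I error without it .039 / .026.
- All available cases, adding 8 session-1-only records: offset .015 / .024 SD at 18:16 and .029 / .049 SD at 19:15.

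**Check with fitted mixed models** (maximum likelihood, 150 data sets, 17:17, π = .5). The mean estimate is .494 in all three models. The standard error is .171 for condition + order, .147 with session added, and .147 for effect-coded condition × order.

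**The case against.** The strongest reply is that the within/between wording is the language of a mixed factorial design, which is commonly fitted with the interaction, and that including order at all suggests the authors had sequence effects in mind. On that reading there is no loss. The full model may also be given in the grant application, which is listed as an attachment and is not available here. This stands as far as it goes: the point is an ambiguity, not a demonstrated error. But the text does not name the interaction, and mixed-model software does not always add it by default.

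Second, the harm needs a session change that the documents do not quantify. At .1 to .2 SD the loss is about a point of power or less. That is correct, and the .3 and .5 SD figures are illustrations.

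Third, at r = .60 the average power still exceeds the planned .80, the test is conservative, and bias averages to zero under random loss. The low values at 18:16 and 19:15 apply in one direction only and have better mirror images, and the documents give no evidence of order-related dropout. All of this stands and limits how serious the point is. It does not extend to the reading that reproduces N = 34, where main-effects power falls below .80.

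**Conclusion.** The concern holds, conditionally as stated. As literally written, the model has two factors, neither of which can absorb a session change. Under that reading the drug test is conservative and loses power: on average from .883 to .859 at an assumed .3 SD change and to .811 at .5 SD, given τ = .5 SD, r = .60, 34 completers and random loss from 21:21. Type I error stays at or below about .05 for splits up to 20:14. The estimate is shifted only conditional on an unequal split, in either direction.

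Confidence is medium, because the intended model and the size of any session change are both unknown. The point should still be fixed: prespecification ought to settle which model is fitted, and naming the term costs almost nothing.

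**What to change.** State the fixed effects as condition, session (1/2) and order, with a subject random intercept on all available cases, and take the drug effect from the condition term. Report the number of completers in each order.

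If the factorial form was intended, say that the condition-by-order interaction is included and that the drug effect is the equal-weight marginal condition effect.

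The text should not claim that the session term separates a session effect from differential carryover; in this design it does not.

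The cost is one line of wording and one degree of freedom. No additional data are needed.

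### Maximum likelihood with about 34 crossover pairs and no stated degrees-of-freedom method makes the drug test slightly anti-conservative; REML with a small-sample df method removes this at almost no cost

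*Combined protocol and SAP*

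**What the plan says.** Section II, Data Analysis/Statistical Considerations (under PROJECT DATA), says that primary and secondary outcomes will be evaluated with "mixed linear effects models with condition (lorcaserin, placebo) as a within-subjects factor and medication order as a between-subjects factor". On estimation it says: "Maximum likelihood estimation will be used to account for missing data by analyzing all available cases". The same model is carried over to the impulsivity and reward-bias outcomes.

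The power paragraph of that section uses "an alpha level of .05" and states: "we will recruit a sample of 42 smokers in order to arrive at a final sample of 34 (allowing for up to 20% attrition"). Section II, Participant Enrollment, instead describes a "final sample of 42 eligible participants who complete all study sessions".

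The documents do not mention REML, the test statistic for the drug effect, the degrees-of-freedom method or any small-sample correction. A period (condition-by-order) term is neither stated nor excluded.

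**The concern.** ML estimates the residual variance by dividing the sum of squares by the number of units, without subtracting the fixed effects that have been fitted. In a large trial this is invisible. With 34 pairs it makes the standard error of the drug contrast too small, so p-values and confidence intervals come out slightly too favourable.

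Because no reference distribution is named, an analyst may also use a normal approximation, which adds to the error in the same direction. At stake is whether the .05 level behind the power statement is the level the analysis delivers, and whether a borderline primary result could turn on an unstated software option.

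The reason given for ML is that it uses all available cases. REML does so equally, so that reason does not favour ML.

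**Working it through.** **Inputs from the documents** (Data Analysis/Statistical Considerations unless noted): ML estimation; condition and medication order as factors; alpha .05; power .80; correlation 0.60; two time-points; 42 recruited and 34 analysed. Participant Enrollment gives 42 completers.

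**Assumptions, not in the documents:** two-sided tests; normal errors; a medium effect taken as f = 0.25 (d = 0.5); the period term; and the choice of t, likelihood-ratio or z test.

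**Step 1. The plan's own figure.** The plan says "our power analyses assumed a medium effect size" without giving a number. For a two-level within-subject factor, λ = f² × N × 2 / (1 − ρ).
- At N = 34, ρ = 0.60: λ = 0.0625 × 34 × 2 / 0.40 = 10.63. With critical F(1,33) = 4.14, power is 0.886. N for .80 power is 28.
- At N = 34, ρ = 0.50: λ = 8.5 and power is 0.808.

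So 34 is not reproduced as the minimum N at the stated correlation. It matches ρ = 0.50. The plan calls its figure conservative, and 34 is enough under these assumptions. On attrition, 42 × 0.8 = 33.6, which rounds to 34.

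**Step 2. Bias in the variance.** With n complete pairs and p within-person fixed effects, ML uses SS/n where the unbiased estimate is SS/(n − p).
- Condition and order only (p = 1): 33/34 = 0.971; SE ratio √0.971 = 0.985, so the SE is 1.5% too small.
- With a period term (p = 2): 32/34 = 0.941; SE ratio √0.941 = 0.970, so the SE is 3.0% too small.

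**Step 3. Type I error.** The ML statistic is a t variable on n − p df multiplied by √(n/(n − p)). The true rejection rate is therefore P(|t(n−p)| > crit × √((n − p)/n)). The likelihood-ratio test rejects when n × ln(1 + t²/(n − p)) > 3.841.

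Worked case, n = 34:
- t reference, p = 1: 2.035 × 0.985 = 2.004, and P(|t33| > 2.004) = 0.0533.
- z reference, p = 2: 1.960 × 0.970 = 1.901, and P(|t32| > 1.901) = 0.0663.

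| Test, nominal 5% | n = 34, p = 1 | n = 34, p = 2 | n = 42, p = 1 | n = 42, p = 2 |
|---|---|---|---|---|
| ML, t on n − p df | 5.33% | 5.68% | 5.27% | 5.55% |
| ML, likelihood ratio | 5.53% | 5.92% | 5.43% | 5.73% |
| ML, Wald z | 6.21% | 6.63% | 5.97% | 6.30% |
| REML, z | 5.85% | 5.88% | 5.68% | 5.70% |
| REML, t on n − p df | 5.00% | 5.00% | 5.00% | 5.00% |

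An ML t test on the more generous 2n − 4 = 64 df at n = 34 gives 5.75% and 6.15%, inside the range shown.

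**Step 4. Separating the two causes at n = 34.**
- ML against REML, t reference: 5.33 − 5.00 = 0.33 points (p = 1) and 5.68 − 5.00 = 0.68 points (p = 2).
- ML against REML, z reference: 6.21 − 5.85 = 0.36 points and 6.63 − 5.88 = 0.75 points.
- Normal reference alone (REML with z): 0.85 and 0.88 points.

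In the worst case, 0.88 of the 1.63-point excess is therefore the normal reference and 0.75 is ML.

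**Step 5. Check with dropouts.** A simulation used 42 randomised, 34 with both sessions, 8 with the first session only, correlation 0.60, no drug effect and 4000 runs per model (Monte Carlo SE about 0.35 points). Results for p = 1 and p = 2:
- ML variance ratio: 0.975 and 0.941.
- ML with z: 6.1% and 6.6%.
- ML with t: 5.1% and 5.7%.
- REML with t: 4.9% and 5.1%.

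These agree with the exact figures within simulation error.

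**The case against.** The strongest reply is that the ML sentence concerns missing data. It may mean likelihood-based analysis in general, as opposed to deleting incomplete cases, and need not be a deliberate choice of ML over REML. That reading is possible, but an analyst who follows the text literally would fit ML, so the wording still needs correcting.

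A reader might infer that the drug test has a true error rate of 6.6% and that ML is the cause. The documents do not support this. The Wald z test is not in the plan, the period term is not stated, and more than half of the 6.6% excess comes from the normal reference, which REML shares. With condition and order only and a t reference, the rate is 5.3%.

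Three further replies stand:
- If 42 people complete, as Participant Enrollment has it, the range narrows to 5.3% to 6.3%.
- Resistance time is capped at 50 minutes and smoking is counted in half cigarettes from a tray of eight. Departures from normality could matter as much as a 1.5% to 3.0% error in the SE, so the decimals should not be read as the trial's exact error rate.
- Power is not threatened: it is 0.886 at N = 34 under the assumed f = 0.25.

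These limit the size of the problem. They do not change its direction, because every ML variant calculated exactly exceeds 5%.

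**Conclusion.** The point holds as a minor one. At 34 complete pairs, the named estimator makes standard errors 1.5% to 3.0% too small. Under normal errors and two-sided testing, type I error lies between 5.3% and 6.6%, depending on a test and a model term that the plan leaves open. About 0.3 to 0.75 points are due to ML; any further excess depends on the reference distribution used.

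The bias is anti-conservative for both primary outcomes and for the secondary outcomes run in the same model, and it buys nothing in the handling of missing data. It is not a serious threat to validity, and nothing in the documents shows that a conclusion would change because of it.

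**What to change.** Replace the ML sentence with:

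*Models will be fitted by restricted maximum likelihood using all available cases, with Kenward-Roger (or Satterthwaite) degrees of freedom for tests and confidence intervals.*

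Both parts are needed: REML with a normal reference would still reject about 5.9% of the time at n = 34. State in the same place whether a period term is fitted, since that sets the degrees of freedom at 33 or 32. Keep ML only for likelihood-ratio comparisons of fixed effects, if any are planned. The 34 and 42 completers should also be reconciled, although this point does not depend on which is meant.

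The cost is a sentence or two and slightly wider intervals. No extra data or participant burden is involved.
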